#### **7.3.14.3. Personal and Social Performance Scale**

The investigator or designee will complete the 5-point Personal and Social Performance (PSP) ([Appendix G](#)) scale ([Patrick, Burns et al. 2009](#)) at the time points identified in [Table 1](#).

#### **7.3.14.4. Heinrichs-Carpenter Quality of Life Scale**

The QLS is a clinician-rated scale that is used to assess health-related quality of life and functioning in patients with schizophrenia during the preceding 4 weeks ([Heinrichs, Hanlon et al. 1984](#)) ([Appendix H](#)). The QLS consists of 21 items in 4 major domains (Intrapsychic Foundations, Interpersonal Relations, Instrumental Role, and Common Objects and Activities). Following a semi-structured interview, each item is rated on a 7-point scale, from 0 (severe impairment) to 6 (normal or unimpaired functioning). The QLS will be completed at the time points specified in [Table 1](#).

### 7.3.14.5. Negative Symptom Assessment-16

The Negative Symptom Assessment is a clinician-rated scale that is used to evaluate the presence, severity, and range of the negative symptoms that often impact the quality of life of those with schizophrenia (Axelrod, Goldman et al. 1993) ([Appendix I](#)). The NSA-16 consists of 16 items with 5 domains (Communication, Emotion/Affect, Social Involvement, Motivation, and Retardation). Each item is rated on a 6-point scale that ranges from 1 to 6 with higher scores indicating more severe pathology. The NSA-16 will be completed at the time points specified in [Table 1](#).

### 7.3.14.6. Modified Medication Satisfaction Questionnaire

The Modified MSQ ([Appendix J](#)) is a 3-item self-report patient satisfaction questionnaire which assesses the level of patient satisfaction with medication. Subjects rate their satisfaction with their current medication, their preference for their current medication versus the one taken prior to the study, and their opinion on the side effects of their current medication versus the one taken prior to the study. Ratings are on a 5-point Likert scale. The Modified MSQ will be collected at the time points identified in [Table 1](#).

## 7.3.15. Other Assessments

### 7.3.15.1. Sixth edition of the Treatment Services Review (TSR-6)-Modified for Mental Health

The modified TSR-6 ([Appendix K](#)) is a brief structured interview to assess specific services provided to patients; this version was modified for use in a patient population for chronic mental illness. The modified TSR-6 focuses on services for five potential problem areas: medical condition, employment and support, legal status, family/social relations, and psychiatric function. Patients are asked about the services that they received in the past 28-42 days. The modified TSR-6 consists of 22 items; it will be administered at the time points identified in [Table 1](#).

### 7.3.15.2. Caregiver Quality of Life – Burden Dimensions (7D) and Visual Analog Scale

The CarerQOL-7D and VAS ([Brouwer, van Exel et al. 2006](#)) ([Appendix L](#)) measures care-related quality of life in informal caregivers. The burden component utilizes 7 items to assess burden, and the valuation component uses a VAS to ascertain level of happiness. The burden items require caregivers to indicate whether they have ‘no’, ‘some’ or ‘a lot’ of problems or fulfillment/ support regarding the given dimension. For problem-related items, ‘no’, ‘some’ and ‘a lot’ are scored 3, 2, and 1, respectively. For fulfillment/support items, reverse scoring applies, so a high score indicates a high level of burden. The valuation component allows for the calculation of a score from 0 (completely unhappy) to 10 (completely happy). The CarerQOL-7D and VAS will be completed by the designated caregiver at the time points identified in [Table 1](#).

### 7.3.15.3. Burden Assessment Scale

The Burden Assessment Scale ([Appendix M](#)) is a 19-item scale completed by the caregiver that focuses on specific subjective and objective consequences of families caring for individuals with severe mental disorders ([Reinhard, Gubman et al. 1994](#)). Respondents are required to indicate

whether they have experienced each of the types of burden - 'Not at all', 'A little', 'Some' or 'A lot' - in the past four weeks. These are scored 1, 2, 3, and 4 respectively. A higher score indicates more perceived burden. The Burden Assessment Scale will be completed by the designated caregiver at the time points identified in [Table 1](#).

#### **7.3.15.4. Birchwood Insight Scale (BIS)**

The BIS ([Appendix N](#)) is an 8-item self-report measure addressing the three components of insight: awareness of illness, relabeling of symptoms (ie, attribution of one's symptoms as part of one's disorder), and need for treatment ([Birchwood, Smith et al. 1994](#)). Possible responses of "agree," "unsure," or "disagree" are scored on a Likert-type scale ranging from 0 to 2. The total score will be summed for a BIS total score (range = 0-16), with higher scores indicating greater insight. The BIS will be completed by the subject at the time points identified in [Table 1](#).

#### **7.3.15.5. New York Assessment of Adverse Cognitive Effects of Neuropsychiatric Treatment subscales**

The NY-AACENT subscales ([Appendix O](#)) are used to detect changes in cognitive function subsequent to pharmacological or similar treatments for neurological or psychiatric problems ([Opler, Antonius et al. 2015](#)). It is comprised of seven items for the patient, seven items for the caregiver, and seven items for the clinician derived from these seven domains: speed of processing, attention/vigilance, working memory, verbal learning, visual learning, reasoning and problem solving, and social cognition. The NY-AACENT will be administered at the time points identified in [Table 1](#).

#### **7.3.15.6. MINI International Neuropsychiatric Interview – Modules I and J**

The MINI is a short, clinician-administered, structured diagnostic interview for making DSM-5 diagnoses ([Appendix P](#)). The MINI has been validated against the much longer Structured Clinical Interview for DSM diagnoses (SCID-5). Modules I (Alcohol Use Disorder) and J (Substance Use Disorder) from the MINI will be administered as shown in [Table 1](#).

### **7.4. Study Requirements and Restrictions**

#### **7.4.1. Prohibited Medications**

Concomitant use of potent oral CYP3A4 inhibitors **and** CYP2D6 inhibitors is to be avoided. In addition, subjects with known CYP2D6 poor metabolism should not receive strong oral CYP3A4 inhibitors during the study. During the study, dose adjustment may be necessary in the event of potent oral CYP2D6 inhibitor, or a CYP3A4 inhibitor or inducer, use. For example, the use of CYP3A4 inducers may require dose escalation. Investigators should consult the Medical Monitor for questions regarding any such dose adjustments. A list of common CYP3A4 inducers or inhibitors and CYP2D6 inhibitors is provided in [Appendix Q](#).

#### **7.4.2. Contraception and Pregnancy**

All male and female subjects must agree to use an acceptable method of contraception for the duration of the study unless they are surgically sterile or post-menopausal (see below). The following are considered acceptable methods of contraception:

1. Double-barrier protection (eg, a condom with spermicide or a diaphragm with spermicide)
2. Intrauterine device (IUD)
3. Oral contraceptive pills or other hormonal methods (eg, a vaginal ring, contraceptive patch, contraceptive implant)

Subjects who are abstinent are eligible, provided they agree to use an acceptable contraceptive method should they become sexually active.

Subjects who are surgically sterile are exempt from the requirement to use contraception. Women who have undergone a hysterectomy, bilateral tubal ligation, or bilateral salpingo-oophorectomy are considered surgically sterile. Men who have undergone a vasectomy or bilateral orchectomy are considered surgically sterile. Partner vasectomy is not considered an approved acceptable method of contraception for a female subject.

Women who are postmenopausal are also exempt from the requirement to use contraception. For the purpose of this study, postmenopausal is defined as the permanent cessation of menstruation for at least 12 months prior to screening in women who are 45 years of age or older.

If a subject becomes pregnant while participating in the study, she will be discontinued from study drug immediately. Pregnancy is not considered an AE, however pregnancy, whether a female study subject or the partner of a male study subject, must be immediately documented on a Pregnancy Form and faxed to **PPD** at the SAE reporting fax number ([Section 13.5](#)) within 24 hours of the investigator becoming aware of the pregnancy. Additional follow-up may be required.

## 8. TREATMENT OF SUBJECTS

### 8.1. Study Drug Dose and Administration

The initial dose of aripiprazole lauroxil will be selected according to the investigator's judgment and will be prepared and administered in accordance with the Directions for Use.

Depending on individual patient's needs, treatment with aripiprazole lauroxil can be initiated at a dose of 441 mg, 662 mg or 882 mg administered monthly, which corresponds to 300 mg, 450 mg and 600 mg of aripiprazole, respectively. Treatment may also be initiated with the 882 mg dose every 6 weeks.

Subjects will receive their first dose of aripiprazole lauroxil no earlier than one week and not later than 6 weeks following their previous dose of injectable risperidone or paliperidone. Due to safety concerns and the potential for rapid emergence of adverse events including akathisia, dystonia and EPS, oral aripiprazole dosing for 21 days after the initial dose of aripiprazole lauroxil is not recommended. Cross-tapering patients from long acting injectable risperidone or paliperidone palmitate to aripiprazole lauroxil is facilitated by the gradual disappearance of plasma risperidone/paliperidone while aripiprazole is concomitantly released from the initial IM aripiprazole lauroxil injection.

Administer aripiprazole lauroxil either in the deltoid muscle (441 mg dose only) or gluteal muscle (441 mg, 662 mg or 882 mg). See Table 3.

**Table 3: Aripiprazole Lauroxil Dosing Frequency and Site of Injection**

Dose	Dosing Frequency	Site of Intramuscular Injection
441 mg	Monthly	Deltoid or Gluteal
662 mg	Monthly	Gluteal
882 mg	Monthly or every 6 weeks	Gluteal

During the course of the study, the PI may adjust the dose of aripiprazole lauroxil. Stepwise dose decreases will be allowed for tolerability, accounting for the slow and prolonged release of aripiprazole lauroxil. Increased dose or frequency (e.g. to monthly from every 6 weeks) may be considered for inadequate efficacy. To allow for the gradual stepwise increase in aripiprazole levels with initial injections, dose increases may be performed after the second injection. Schedule changes, from monthly to every 6 weeks (or the reverse) will also be allowed after the second injection. Dose changes due to the medical need to initiate concomitant CYP modulators may be performed at any time if the concomitant medication is necessary for more than 2 weeks.

After the first change, further dose or schedule changes should be made in consultation with the **PPD** Medical Monitor and must account for the gradual increase in plasma aripiprazole levels following the initial monthly doses.

Table 4 outlines the recommended starting dose for subjects who have been historically stabilized on oral aripiprazole:

**Table 4: Aripiprazole Lauroxil Doses Based on Oral Aripiprazole Total Daily Dose**

Oral Aripiprazole Dose	Intramuscular Aripiprazole Lauroxil Dose
10 mg	441 mg
15 mg	662 mg
20 mg or higher	882 mg

## 8.2. Missed Doses

When a dose is missed, administer the next injection of aripiprazole lauroxil as soon as possible. If the time elapsed since the last aripiprazole lauroxil injection exceeds the length of time noted in Table 5, use oral aripiprazole supplementation with the next aripiprazole lauroxil injection as recommended below.

**Table 5: Recommendation for Concomitant Oral Aripiprazole Supplementation Following Missed Dosesa**

Dose of Patient's Last Aripiprazole Lauroxil Injection	Length of Time Since Last Injection		
	No Oral Supplementation Required	Supplement with 7 Days Oral Aripiprazole	Supplement with 21 Days Oral Aripiprazole
Monthly 441 mg	≤ 6 weeks	> 6 and ≤ 7 weeks	> 7 weeks
Monthly 662 mg	≤ 8 weeks	> 8 and ≤ 12 weeks	> 12 weeks
Monthly 882 mg	≤ 8 weeks	> 8 and ≤ 12 weeks	> 12 weeks
882 mg every 6 weeks	≤ 8 weeks	> 8 and ≤ 12 weeks	> 12 weeks

a Oral aripiprazole supplementation dosage may be per Table 4.

## 8.3. Early Dosing

The aripiprazole lauroxil injection should not be given earlier than 14 days after the previous injection.

## 8.4. Dose Adjustments for CYP450 Considerations

In subjects taking strong CYP2D6 or CYP3A4 modulators the initial and subsequent dose of aripiprazole lauroxil should be selected based upon the recommendations of Table 6 below.

Once stabilized on aripiprazole lauroxil, refer to the dosing recommendations below for patients taking CYP2D6 inhibitors, CYP3A4 inhibitors, or CYP3A4 inducers:

- No dosage changes recommended for aripiprazole lauroxil, if CYP450 modulators are added for less than 2 weeks.
- Make dose changes to aripiprazole lauroxil if CYP450 modulators are added for greater than 2 weeks (see Table 6).

**Table 6: Aripiprazole Lauroxil Dose Adjustments with Concomitant CYP450 Modulator Use**

Concomitant Medicine	Dose Change for ARIPIPRAZOLE LAUROXIL a
Strong CYP3A4 Inhibitor	Reduce the dose of ARIPIPRAZOLE LAUROXIL to the next lower strength. No dosage adjustment is necessary in patients taking 441 mg ARIPIPRAZOLE LAUROXIL, if tolerated. For patients known to be poor metabolizers of CYP2D6: Reduce dose to 441 mg from both higher doses. No dosage adjustment is necessary in patients taking 441 mg ARIPIPRAZOLE LAUROXIL, if tolerated.
Strong CYP2D6 Inhibitor	Reduce the dose of ARIPIPRAZOLE LAUROXIL to the next lower strength. No dosage adjustment is necessary in patients taking 441 mg ARIPIPRAZOLE LAUROXIL, if tolerated. For patients known to be poor metabolizers of CYP2D6: No dose adjustment required.
Both Strong CYP3A4 Inhibitor and Strong CYP2D6 Inhibitor	Avoid use for patients at 662 mg or 882 mg dose. No dosage adjustment is necessary in patients taking 441 mg ARIPIPRAZOLE LAUROXIL, if tolerated. For patients known to be poor metabolizers of CYP2D6: Same as for extensive metabolizers.
CYP3A4 Inducers	No dose adjustment for 662 mg and 882 mg dose, increase the 441 mg dose to 662 mg. For patients known to be poor metabolizers of CYP2D6: Same as for extensive metabolizers.

a For the 882 mg dose administered every 6 weeks, the next lower strength should be 441 mg administered every 4 weeks.

Augmentation with oral antipsychotics is permitted per clinical judgment and should be recorded as a concomitant medication separately from other concomitant medications.

Sites must have written procedures in place detailing the healthcare personnel required to be on site during subject dosing, the availability of equipment and medications necessary to treat an emergency (should it occur), and the process for transferring a subject to a medical facility if necessary.

## **8.5. Oral Aripiprazole Test Doses**

Oral aripiprazole for use as test doses during screening is an approved antipsychotic marketed under the trade name Abilify® ([Bristol-Myers Squibb 2016](#)). The first test dose will be administered in the clinic.

Oral test doses of aripiprazole are in 5 mg tablet form. Oral aripiprazole tablets must be kept in a locked storage area before dosing and must be stored in accordance with the full prescribing information for Abilify.

Aripiprazole for use as oral aripiprazole test doses will be commercially available Abilify® 5 mg tablets ([Bristol-Myers Squibb 2016](#)) or aripiprazole obtained from a local commercial source, provided in commercial packaging provided to the site by Alkermes.

## **8.6. Treatment Adherence**

All study drug injections will be directly administered by clinical study staff. Study staff will address non-adherence with the subject as needed.

## **8.7. Blinding**

Not applicable. The study is open-label.

## **9. STUDY DRUG MATERIALS AND MANAGEMENT**

### **9.1. Study Drugs**

The product in this study is aripiprazole lauroxil, a covalently bonded modification of aripiprazole to form *N*-lauroyloxymethyl aripiprazole.

Detailed information about aripiprazole lauroxil can be found in the [Aripiprazole Lauroxil Investigator's Brochure \(IB\)](#).

### **9.2. Accountability**

The clinical site is required to maintain current drug dispensation and accountability logs throughout the study. All unused supplies will be checked against the drug movement records during the study and/or at the end of the study.

### **9.3. Handling and Disposal**

Following completion and verification of accountability logs, all unused and used packages must be destroyed. Packages may be destroyed on site according to Good Clinical Practice (GCP) and site practice. Alternatively, the sponsor may arrange for destruction with a third party vendor operating in accordance with GCP and/or Good Manufacturing Practice (GMP), as applicable.

## **10. ASSESSMENT OF EFFICACY**

Efficacy will be evaluated based on Clinical Global Impressions-Severity (CGI-S) and Brief Psychiatric Rating Scale (BPRS) responses.

## **11. QUALITY OF LIFE, DAILY AND SOCIAL FUNCTIONING**

The following assessments will be collected to characterize any change in quality of life, including daily and social functioning, after treatment with aripiprazole lauroxil:

- Heinrichs-Carpenter Quality of Life Scale (QLS)
- Negative Symptom Assessment-16 (NSA-16)
- Sexual functioning subscale from UKU Side Effect Rating Scale and CSFQ scores
- Personal and Social Performance scale (PSP)
- Total and individual items scores of the Modified MSQ

## 12. OTHER ASSESSMENTS

The following assessments will be collected to explore potential changes in healthcare burden, cognition, insight, and psychosocial care needs following a transition to aripiprazole lauroxil:

- Health economics
  - Total healthcare costs as measured by TSR-6-Modified for Mental Health
- Functional Assessment
  - BIS
- Family Measures
  - CarerQOL-7D and VAS
  - Burden Assessment Scale
- Investigator- and Caregiver-Rated Cognition
  - Respective NY-AACENT subscales
- Substance Use
  - M.I.N.I. Module I (alcohol use disorder)
  - M.I.N.I. Module J (substance use disorder)

## 13. ASSESSMENT OF SAFETY AND TOLERABILITY

The following safety and tolerability measures will be assessed throughout the study and summarized:

- AEs
- Injection site reactions
- Vital signs (blood pressure, heart rate, respiratory rate, and body temperature), and waist circumference and weight
- Clinical laboratory parameters (chemistry [including prolactin], hematology, and urinalysis) ([Table 2](#))
- C-SSRS responses
- ESRS-A scores

### 13.1. Definition of Adverse Event

An AE is any untoward medical occurrence in a patient or clinical investigation subject administered a pharmaceutical product. The occurrence, which may or may not have a causal relationship with the treatment, may include any clinical or laboratory change that does not commonly occur in that subject and is considered clinically significant.

Illnesses present prior to the subject signing the informed consent form (ICF) are considered to be pre-existing conditions and are documented on the medical history eCRF. Pre-existing conditions that worsen during the study are entered on the AE eCRF.

All out-of-range laboratory values will be deemed as clinically significant or not clinically significant by the investigator. Clinically significant values will be considered AEs and recorded as such on the eCRFs.

Pregnancy alone is not considered an AE, although a female subject will be withdrawn from study drug treatment if a pregnancy occurs. If a pregnancy occurs in the partner of a male subject, it is not required that the male be withdrawn from study drug; however, contraceptive requirements should be revisited. As described in [Section 7.4.2](#), the pregnancy must be reported to Alkermes and additional follow-up may be required.

### 13.2. Definition of Serious Adverse Event

An SAE is any AE, occurring at any dose and regardless of causality that:

- Results in death
- Is life-threatening. The subject is at immediate risk of death from the reaction as it occurs. This does not include reaction that, had it occurred in a more severe form, might have caused death.

- Requires inpatient hospitalization or prolongation of existing hospitalization. Hospital admission for elective surgery scheduled prior to study entry is not considered an SAE.
- Results in disability/incapacity (eg, a substantial disruption of a person's ability to conduct normal life functions)
- Is a congenital anomaly/birth defect

Important medical events that may not result in death, be immediately life threatening, or require hospitalization may be considered to be SAEs when, based upon appropriate medical judgment, they may jeopardize the patient or subject and may require intervention to prevent one of the other outcomes listed above.

### **13.3. Relationship to Study Drug**

The assessment of study drug relationship to each AE will be reported on the appropriate source document (and SAE form, in the event of an SAE) by the investigator (or designated sub-investigator) according to his/her best clinical judgment. The criteria listed in [Table 7](#) should be used to guide this assessment. Please note that not all criteria must be present to be indicative of a particular drug relationship. All study drugs are considered “test drugs” for the purposes of the definitions listed in the table.

**Table 7: Adverse Event Causality Guidelines**

Relationship	Criteria for assessment
Definitely related	
There is evidence of exposure to the test drug. AND The temporal sequence of the AE onset relative to administration of the test drug is reasonable. The AE is more likely explained by the test drug than by another cause. Dechallenge (if performed) is positive. Rechallenge (if feasible) is positive. The AE shows a pattern consistent with previous knowledge of the test drug or test drug class.

Probably related	
There is evidence of exposure to the test drug. AND The temporal sequence of the AE onset relative to administration of the test drug is reasonable. The AE is more likely explained by the test drug than by another cause. Dechallenge (if performed) is positive.

Possibly related	
There is evidence of exposure to the test drug. AND The temporal sequence of the AE onset relative to administration of the test drug is reasonable. The AE could have been due to another equally likely cause. Dechallenge (if performed) is positive.

Probably not related	
There is evidence of exposure to the test drug. AND There is another more likely cause of the AE. Dechallenge (if performed) is negative or ambiguous. Rechallenge (if performed) is negative or ambiguous.

Definitely not related	
The subject did not receive the test drug. OR Temporal sequence of the AE onset relative to administration of the test drug is not reasonable. OR There is another obvious cause of the AE.

### 13.4. Monitoring and Recording of Adverse Events

AE data collection will begin after a subject signs the ICF and will continue until completion of the End of Treatment/Early Termination visit (Day 169). Any AE or SAE having an onset after the End of Treatment/Early Termination visit will not be collected or reported unless the investigator feels that the event may be related to the study drug.

Subjects will be instructed by the investigator or designee to report the occurrence of any AE. All volunteered, elicited, and observed AEs are to be recorded on the AE eCRFs.

The investigator will assess all AEs regarding any causal relationship to the study drug (see [Section 13.3](#)), the intensity (severity) of the event, action taken, and subject outcome.

The following criteria should be used to guide the assessment of intensity (severity):

- **Mild:** Causes awareness of sign or symptom, but is easily tolerated; does not interfere with usual activities
- **Moderate:** Causes discomfort enough to interfere with usual activities
- **Severe:** Is incapacitating; results in inability to work or perform usual activities

[figure not shown]
All AEs will be followed until resolution, until deemed stable by the investigator, or until the subject is deemed by the investigator to be lost to follow-up.

For clinical study safety reporting purposes, the most recent version of the Investigator's Brochure will be used as the reference document to designate event expectedness.

Withdrawal from the study as a result of an AE and any therapeutic measures that are taken shall be at the discretion of the investigator. If a subject withdraws from the study for any reason, any ongoing AEs will be followed until resolution, until deemed stable by the investigator, or until the subject is deemed by the investigator to be lost to follow-up.

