### 6.3. Subject Withdrawal

A subject may be discontinued from the study at any time if the subject, investigator, or sponsor determines that it is not in the best interest of the subject to continue participation. Reasons for discontinuation include:

- AE
- Lost to follow-up
- Lack of Efficacy
- Withdrawal by subject
- Non-compliance with study drug
- Other
- Pregnancy
- Protocol deviation
- Study terminated by sponsor

Subjects completing all visits up to and including Day 169 will be considered completers.

If a subject withdraws from the study for any reason, any ongoing AEs will be followed until resolution, until deemed stable by the investigator, or until the subject is deemed by the investigator to be lost to follow-up. If, in the opinion of the investigator, it is necessary to monitor a subject beyond the final study visit, the study period may be extended as necessary. In such instances, the sponsor and the investigator will agree to an acceptable schedule.

In the event that a subject chooses to withdraw from the study, the investigator should make a reasonable effort to ascertain the reason(s) for withdrawal, while fully respecting the subject's rights. Subjects are to be asked to return to the clinic for an ET visit. If the subject fails or refuses to return to the study center, an attempt must be made to contact the subject by telephone in order to assess as many safety and efficacy parameters as possible. All data collected over the telephone must be documented and kept in the subject's record.

The investigator must maintain a record of all subjects who fail to complete the study. The reason for study discontinuation will be made on the appropriate electronic case report form (eCRF). If a subject is lost to follow-up, a reasonable attempt to contact the subject must be made and documented.

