### 7.3.12. Adverse Event Monitoring

AEs will be monitored continuously from the time a subject signs the informed consent document until the completion of the final study visit (see [Table 1](#)). AEs and serious adverse

events (SAEs) are defined in [Section 13.1](#) and [13.2](#), respectively. [Section 13.4](#) provides guidance on the monitoring and reporting requirements for AEs. [Section 13.5](#) provides guidance on the reporting requirements for SAEs.

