### **3.7. Safety and other Analysis**

#### **3.7.1. Adverse Events**

Summaries will be presented by treatment group and overall.

Adverse events will be coded using the Medical Dictionary for Regulatory Activities (MedDRA) version 19.0. Treatment-emergent AEs (TEAEs) are defined as AEs that are newly occurring or worsening from the time of the first dose of study drug.

An overview table, including number of subjects with any TEAEs, serious adverse events (SAEs), study drug related TEAEs, TEAE by severity, and AE leading to discontinuation will be summarized.

In addition, the TEAEs will be summarized for the following:

- TEAEs by System Organ Class (SOC) and Preferred Term (PT)
- TEAEs by SOC, PT, and severity
- Drug Related TEAEs by System Organ Class and Preferred Term
- SAEs by System Organ Class and Preferred Term
- AEs leading to discontinuation by System Organ Class and Preferred Term

A subject having the same AE (as determined by the coded MedDRA preferred term) more than once will be counted only once in the number and percentage of subjects' calculation for that AE. Similarly, if a subject had more than one AE in a System Organ Class, the subject will be counted only once in the number of subjects with an AE for that System Organ Class. If a subject has the same AE on multiple occasions, the highest severity (severe > moderate > mild) recorded for the event will be presented in the AEs by severity table. Treatment-related AEs are defined as those events with a 'Relationship to Study Treatment' recorded on CRF as 'Definitely Related', 'Probably Related' or 'Possibly Related', others will be not related AEs.

Listings for all AEs, SAEs, and AEs leading to discontinuation will be presented.

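### Routine collection of new AEs and SAEs ends at the EOT/ET visit, apart from events the investigator suspects are drug-related, and no follow-up is counted from the last injection

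*Protocol*

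**What the plan says.** - **Protocol 13.4** sets the cut-off: "Any AE or SAE having an onset after the End of Treatment/Early Termination visit will not be collected or reported unless the investigator feels". The condition in full is "unless the investigator feels that the event may be related to the study drug".
- **Protocol 7.3.12** places the end of monitoring at the same point: it runs from consent "until the completion of the final study visit".
- **Protocol 6.3** covers withdrawal: "Subjects are to be asked to return to the clinic for an ET visit". It does not say how that visit should sit in time relative to the last injection. It provides for telephone assessment if the subject does not come, for follow-up of AEs already under way, and for longer monitoring if the investigator thinks it necessary, on a schedule agreed with the sponsor.
- **Protocol 8.1**, in the text under Table 3, allows stepwise dose decreases "accounting for the slow and prolonged release of aripiprazole lauroxil". It gives no duration for that release.
- **SAP 3.7.1** defines treatment-emergent AEs as those "newly occurring or worsening from the time of the first dose of study drug". There is a start point and no end point. Results are numbers and percentages of subjects, and SAP 3.2.1.1 analyses everyone who received at least one injection.

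**The concern.** The product is a depot, so exposure continues after the subject leaves the clinic. The collection period should therefore depend on when the last injection was given. Here it depends on when the last visit takes place. A completer seen on schedule gets a full dosing interval of observation after the last injection. A subject who withdraws soon after an injection may get only a few days.

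The listed reasons for withdrawal in 6.3 include adverse events, lack of efficacy and non-compliance, so the subjects with the shortest observation may be those whose later course matters most for tolerability. A relapse hospitalisation or suicide attempt two weeks after the ET visit, put down to schizophrenia, would fall outside the collection rule. Safety is part of the primary objective (Protocol 5.1), and the AE tables are its main output.

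**Working it through.** **Inputs**

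- Protocol Table 1: injections 28 or 42 days apart; 6 injections (monthly) or 4 (every 6 weeks); EOT target Day 169; Month 6 window Day 149–183.
- Protocol 13.4 and 7.3.12: routine collection ends at the EOT/ET visit.
- Interval from last injection to ET visit: not stated anywhere. Values of 1, 7 and 14 days are assumed below to show the range.

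**Step 1. Reproduce the plan's injection counts.** Injection days before Day 169 are 1 + 28k or 1 + 42k.

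- Monthly: 1, 29, 57, 85, 113, 141, which is 6 injections.
- Every 6 weeks: 1, 43, 85, 127, which is 4 injections.

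Both match Table 1.

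**Step 2. Completers on target days.** Days collected = EOT day − last injection day.

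- Monthly: 169 − 141 = 28.
- Every 6 weeks: 169 − 127 = 42.

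Each is exactly one dosing interval.

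**Step 3. Completers seen early in the window.** If the last injection is on its target day and the EOT visit is on Day 149:

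- Monthly: 149 − 141 = 8 days.
- Every 6 weeks: 149 − 127 = 22 days.

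Footnote 1 to Table 1 anchors each visit to the one before, which works against this, but the window permits it.

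**Step 4. Early withdrawers.** With the ET visit x days after an injection and a dosing interval D, the part without routine collection is D − x.

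| x (assumed) | D = 28 | D = 42 |
|---|---|---|
| 1 | 27 (27/28 = 96%) | 41 (41/42 = 98%) |
| 7 | 21 (21/28 = 75%) | 35 (35/42 = 83%) |
| 14 | 14 (14/28 = 50%) | 28 (28/42 = 67%) |

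**Step 5. What can still reach the tables after the ET visit.** A new event must pass two filters. The site has to learn of it, with no contact scheduled, and the investigator has to think the drug may be involved. Table 7 in 13.3 puts an event with another obvious cause under definitely not related.

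Because the TEAE definition has no end date, the events that pass join the same tables as the all-cause events recorded up to the visit. The denominator is every injected subject, and no exposure-adjusted rate is planned. A missed event can therefore lower the reported percentage and cannot raise it.

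**The case against.** The strongest reply is that collection does not simply stop, although a reader who takes the first half of the 13.4 sentence alone might infer that it does. Suspected-related events remain reportable, and the bar is low: Table 7 counts an event as possibly related even when another cause is equally likely. Ongoing AEs, including one that prompts withdrawal, are followed. Section 6.3 lets the investigator prolong monitoring, and since 7.3.12 runs to the final study visit, an extension could carry collection with it.

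The study is also single-arm and descriptive, so no comparison with a control is distorted, and nothing in the documents shows that withdrawers have more late events. Collecting all events after the ET visit would bring in some that arise on the next treatment.

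Much of this stands, and it limits the point to routine, all-cause collection. It does not close the gap. The exception works only for events the site hears about and attributes at least possibly to the drug. Follow-up of ongoing AEs does not reach new ones, and the extension is discretionary. Section 13.5 calls for all SAEs to be reported and states no end date, but 13.4 is the specific rule on timing and makes later SAEs conditional on suspected cause. The concern about later treatment is fair and is dealt with in the fix.

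**Conclusion.** The point holds in a limited form. Routine all-cause collection is anchored to a visit, with no minimum time since the last injection. Completers on target days have 28 or 42 days. Early withdrawers have no floor, and a completer seen at the start of the Month 6 window could have 8 or 22. All-cause TEAE and SAE incidence can be under-counted, and what arrives late is selected by causality opinion. The direction follows from the fixed denominator. The size cannot be given, because the documents state neither a dropout rate nor any ET timing. The 7-day example is an assumption.

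Three stronger readings are not supported:

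- **An eight-week safety window.** Table 5 sets limits of 6 weeks (441 mg) and 8 weeks (662 and 882 mg), and a reader might treat these as exposure periods. They govern oral supplementation when an injection is late. They are not measured release times and do not show that on-schedule completers are followed too briefly.
- **A count of affected subjects.** Any number would rest on an assumed dropout rate and on every ET visit falling within one dosing interval. A subject who withdraws when an injection is due already has a full interval.
- **A contradiction over contraception.** Protocol 7.4.2 says that subjects "must agree to use an acceptable method of contraception for the duration of the study". Because 8.1 gives the prolonged release no duration, nothing in the documents conflicts with this.

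This is a worthwhile and inexpensive improvement to safety ascertainment. It does not invalidate the study.

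**What to change.** **Protocol 13.4, with 7.3.12 aligned.** Collect all AEs and SAEs, whatever the suspected cause, until the later of (a) the EOT/ET visit and (b) one full dosing interval after the last injection: 28 days for monthly dosing or 42 days for dosing every 6 weeks. This gives withdrawers what on-schedule completers already have. The sponsor may justify a longer period. Where the visit falls before (b), make one telephone contact at (b). That includes a completer seen early in the Day 149–183 window. Section 6.3 already accepts telephone safety assessment. Keep the existing suspected-related exception for events after the new cut-off.

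**SAP 3.7.1.** Give the TEAE definition the same end date, list later events separately, and flag events that begin after another antipsychotic has been started. The call should record that start date.

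**Cost.** Amended wording, one call per affected subject, slightly higher AE counts, and a short wait before some subjects' data can be closed. Some events will have occurred on later treatment; the flag lets a reader set them apart but does not settle their cause.
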